PREVUE v4, dd 12Dec2018

PREVUE; PlantaR flexion Exercise for Venous Ulcer Evaluation, a multi-centre, controlled, prospective, randomized feasibility trial

Version 4, dd 12 December 2018

Chief Investigator's Statement of Ownership and Content.

I, [name], confirm that this protocol is my work and is owned by me. The protocol conforms with standards outlined in the Declaration of Helsinki 1964.

Name (PRINT):___[name]_____

Signature:

Date: ____12 Decl 2018_____

RESEARCH PROTOCOL SUMMARY

TITLE:	PREVUE; PlantaR flexion Exercise for Venous leg UlcEr, a multi- centre, controlled, prospective, randomized feasibility trial
Short title:	PREVUE
IRAS number	222694
Device description	StepIt plantar flexion rocker pedal device. CE-marked and licensed medical device. To be used in this study for indicated purpose, namely plantar flexion exercise.
Study design	Single centre, controlled, prospective randomized feasibility trial
Primary objective	To assess the feasibility of conducting a full RCT in the future - Participants' compliance to StepIt exercise regime
	 Recruitment and attrition rates, willingness of patients to be randomised, response rates to questionnaires, and degrees of missing data Testing of eligibility criteria and ability/willingness of clinical staff to partake in recruitment of participants Adequacy of duration of follow-up (e.g. in relation to VLU healing)
Secondary objectives	To determine the acceptability and efficacy of the step-it pedal as an adjuvant therapy for VLU at 6 and 12 weeks post-baseline - Healing rate (ulcer size, PUSH score) - Ankle motion range - Patient mobility score - VLU-related quality of life score - VLU-related pain - Patient feedback on use of the device
Patient population	A total of 28 participants, over the age of eighteen, with venous leg ulcers and treated either in hospital or at home by the community nursing team. Participants must have the capacity to provide informed written consent and complete patient reported outcome measures. Participants are recruited from the local community nursing caseload and identified in hospital clinics. - 12 Patient will receive treatment as usual (TaU) - 12 Patients will receive TaU plus StepIt exercise programme intervention

	Randomisation will be stratified for ulcer size, with cut-off PUSH
	score of up to 8, and 9 and above.
Sponsor	Cumbria Partnership NHS Foundation Trust
Manufactures O foundan	Charalle Coreboure A.D.
Manufacturer & funder	StepIt System AB,

1. LAY SUMMARY

Venous leg ulcers (VLUs) are the most common type of leg ulcers, affecting 1-3% of the population over 60 years and this incidence is expected to increase with an aging population. There is some evidence to suggest that specific exercise of the calf muscle through for example plantar flexion movement with resistance — moving the front of the foot up and down, similar to what a drummer does when using the foot pedal of a drum - may improve the calf muscle pump function. The positive effects have been shown at the haemodynamic level; they have shown that at least in the short-term there is better blood flow and endurance if the calf muscle is exercised in this manner.

It is acknowledged that venous return from the lower limbs depends on an efficient calf muscle pump and adequate range of ankle motion. Whilst failure of these systems may contribute to venous leg ulceration, evidence suggests that exercise programmes designed to increase the strength of the calf muscle pump through resistance training is feasible and effective in improving calf muscle pump function and ankle range of motion. As yet there remains considerable uncertainty as to the effects of an exercise programme on ulcer healing. There is very limited research data available on the medium- to long-term effects of calf muscle exercising by VLU patients on the healing rate of the ulcer.

This study is a prospective, controlled, randomised, feasibility trial to determine if the use of a CE-approved plantar flexion pedal, developed by StepIt Ltd, will be of benefit to people with VLU in terms of healing rate of VLUs. This pilot aims to assess the feasibility of conducting a full randomised clinical trial in the future. Of the total of 48 patients to be recruited, 24 patients will be randomised to treatment as usual, standard compression therapy only, and the other 24 will be allocated to treatment as usual plus a StepIt exercise programme for 12 weeks. The main outcome measure will be the degree of healing of the VLU. Other outcomes measures will include acceptability of the device training, trial completion rates, and ankle range of motion. Patients with VLUs are less mobile than their aged matched population for a variety of reasons. Initiating foot and ankle exercises may be a first step in increasing physical activity for this population and improving calf muscle pump function.

2. INTRODUCTION

Venous leg ulcers (VLUs) are the most common type of leg ulcers, affecting 1-3% of the population over 60 years (SIGN 2010, Graham *et al* 2003) and this incidence is expected to increase with an aging population. A positive relationship has been observed between occurrence and specific modern lifestyle risk factors such as sedentary lifestyles and obesity (Brand *et al* 1998). The natural history of the disease is a continuous cycle of healing and breakdown over decades and VLUs are associated with considerable; expense, morbidity and impaired quality of life (Persoon *et al* 2004).

Table 1 shows annual NHS cost for treating VLUs compared to other chronic wound treatments.

Table 1. Chronic wound treatment costs to the NHS (Posnett & Franks 2008)

	Annual incidence	Cost per patient	Annual NHS cost (2005–2006)
Venous leg ulcers	108,600	£1,500-1,800	£168–198m
Foot ulcers	57,000	£5,200	£300m
Pressure ulcers	410,000	£4,300-6,400	£1.8-2.6bn
TOTAL	575,600	£4,000-5,400	£2.3-3.1bn

Despite extensive research the exact manner in which VLUs develop, is not yet fully understood however it is agreed that prolonged venous hypertension caused by chronic venous insufficiency is a common aetiological factor (Eberhardt & Rafetto 2005, White & Ryjewski 2005). The mainstay of treatment of VLUs is the reversal of venous hypertension through compression bandaging (O'Brien et al 2012), however up to 15-30% do not respond to this current gold standard treatment and remain unhealed even after 6 months of treatment (Moffett et al 2006, O'Meara, Cullum & Nelson 2009).

Venous return is also facilitated by the action of the foot and calf muscle pump but previous studies have shown that patients with VLUs have histopathological changes of degeneration in the calf muscle (Taheri *et al* 1984) and impaired calf muscle function (Porter, 1995, Yang, Vandogen & Stacey 1999). Literature suggests that there is a relationship between VLU severity, calf muscle pump dysfunction and range of ankle movement (Back *et al*.1995, Dixy, Brooke and McCollum, 2003, Davies *et al.*, 2007). Patients with VLU have a limited range of ankle movement because of decreases in both plantar flexion and dorsiflexion. This decreased ankle mobility is associated with delayed VLU healing (Davies *et al.*, 2007).

There is evidence that exercise of specifically the calf muscle can improve physiological functioning of said muscle. Exercises such as heel raises, flexion, extension and rotation of the ankles have been shown to increase venous return (Padberg, Johnston & Sisto, 2004, Roaldsen *et al* 2006, Jull *et al* 2009) and clinical guidelines recommend ankle exercises and walking (RCN 1998, SIGN 2010). There is paucity of studies demonstrating any correlation with exercise and improvement in ulcer healing but the suggestion that exercise as an adjunct therapy may improve the time to VLU healing warrants exploration.

Patients with venous leg ulcers report multiple co-morbidities and are more likely to be sedentary than age matched controls (Persoon *et al* 2004, Roaldsen *et al* 2006). Whilst exercise could be of particular benefit for this group of patients' research suggests that around 50% of sedentary adults who start an exercise programme stop within the first 6 months of involvement (Heinen *et al* 2007). This study will apply a step—it rocker pedal for the first time in patients with VLU's in addition to the standard treatment of compression therapy. This is a small pedal device that can be used from a seated position and was first devised to help alleviate the risk of deep vein thrombosis for travellers on long haul flights. Patients may be receptive to this form of exercise especially if they are elderly, frail, have limited mobility, have a fear of falling or are housebound.

The aim of this initial randomised, controlled, prospective feasibility study is to determine the acceptability and efficacy of the step-it pedal as an adjuvant therapy for VLU with a primary outcome measure of VLU healing. This is a pilot aiming to assess the feasibility of conducting a full randomised clinical trial in the future.

3. INVESTIGATIONAL DEVICE

The step-it pedal is developed at Uppsala University Hospital through collaboration between [name] and vascular surgeon [name]. The step-it rocker pedal is designed to mimic the walking movement and make the foot bend and stretch. This design is aimed to stimulate the calf muscles and increases circulation in the legs, thereby decreasing the risk for blood clotting and circulation problems. The step-it pedal is 95mm by 230mm by 40mm, weights 212 gram and is made out of ABS-plastic with a silicon footpad (figure 1).

Resistance of the pedal is circa 6 kg and cannot be adjusted. There is no recommended tempo indicated for the pedal, simply because some patients will be more able to do the movements. The videos on the Step-It website show a frequency of roughly 1 second downwards, 1 second upwards motion (https://www.youtube.com/watch?v=nsAZm5TxEIY&feature=youtu.be and http://www.stepit.com/). However, in the VLU target population , patients will be encouraged to work at – or towards - a 2 second downwards, 2 second upwards motion frequency.

Figure 1. Step-it pedal

4. STUDY HYPOTHESIS

4.1 Primary objective

To assess the feasibility of conducting a full RCT in the future

4.2 Secondary objective

 To assess the acceptability and efficacy of the Step-It pedal as an adjuvant therapy for VLU healing

5. STUDY PROTOCOL

5.1 Study design and timeline

This concerns a multi-centre, controlled prospective randomized study. The study will be carried out in Cumbria by NHS Cumbria Partnership Foundation Trust, North Cumbria Universit Hospitals NHS trust and North Cumbria CCG. The study will take place in local community setting with support and oversight from community nurses and research staff. Research delivery staff will be delegated to provide support with data collection and processing.

Table 2. Anticipated timeline

Month	Setup	Recruitment	Analysis	Finalise
Mar-17	Submission for			
	HRA approval			
Apr-17	NIHR portfolio adoption			
May-17	HRA and Trust approval	Start recruitment		
Dec-18		Finish recruitment		
Jan-19			Analyze data	
Mar-19				Finalise analysis &
				report

5.2 Participant identification & screening

Patients who are referred to the local community nursing team with a VLU will be screened for eligibility for this study by the local community nursing team. The research team will then be informed on potential participants and the patient information sheet will be added to the appointment letter. All eligible patients will be invited to take part until the required numbers have been achieved. Patients will be recruited sequentially and randomised into two groups: one control group receiving care as usual and one intervention group receiving care with the StepIt device. The eligible patient population is defined in the Inclusion and Exclusion criteria section. Consent

If the community research nurse is not available, arrangements will be made for someone of the research team to join the (non-research) nurse to the first appointment. During this visit the study will be discussed in further detail and the participant has the opportunity to ask questions that they may have. If potential participants meet the eligibility criteria, the patients can be consented by the continence care team or this may be delegated to the research delivery team as long as the patient's verbal consent has been sought for the latter arrangement. A screening form will be completed for potentially eligible patients to confirm that they indeed meet the trial criteria.

Participants will receive no incentives and consent will be regarded as a process and not a one off event. Participants are free to withdraw from the study at any time without the need to give any reasons for withdrawal. Their standard care will not be affected by either declining to participate in the study or withdrawing during participation.

5.3 **Recruitment**

Participants will be randomised to either the control group (standard care) or the intervention group (standard care plus use of a StepIt pedal) for 12 weeks or until ulcer healing has taken place. Patients in both groups will be given the usual leg ulcer information leaflet, but those in the intervention group will be issued with a StepIt Pedal to use daily for foot and ankle exercises. These exercises consist of resisted plantar flexion while seated, performed 2 times daily in the pattern of: 1 minute exercise / 1 minute rest, 10 times (participants may alternate legs as an alternative to merely resting both legs for 1 minute). The participants will be asked to keep an exercise diary to record their activity. At their discharge visits participants are asked to provide their opinion on trial participation. All participants will have demographic data obtained and the following base line measures (table 2):

- VLU size measured with Convatec grid tool
- PUSH score (size and characteristics)
- Mobility score
- Ankle range of motion using a goniometer
- Visual analogue pain score
- Quality of life assessment using the Charing Cross Venous Ulcer Questionnaire

Table 3. Baseline measures

Weeks	0	2	4	6#	8	10	12#
Ulcer size and PUSH score	Х			Χ			Χ
Mobility score	Χ			Х			Χ
Ankle range of motion	Χ			Х			Χ
Visual analogue pain score	Χ			Χ			Χ
Charing Cross Venous Ulcer Questionnaire	Х			Х			Χ

Allowed to be up to 2 weeks early or late

The Pressure Ulcer Scale for Healing (PUSH) tool, see Appendix 1 is a standardised method of assessing and monitoring the severity and healing of both pressure ulcers and venous leg ulcers (Stotts et al, 2001; Ratliff & Rodeheaver 2005). Concerns have been raised regarding the criterion validity and intra-rater reliability of the tool (Pillen et al 2009) however in the absence of other valid tools it provides a comprehensive parallel assessment of the ulcer along with measuring size alone.

A mobility measure will be taken using a life space questionnaire, see Appendix 1 (Stalvey *et al* 1999). This is a tool that has demonstrated reliability and construct and criterion validity in establishing the spatial extent of an older person's mobility within their home setting. There are other versions (Peel *et al* 2005) that additionally measure the use of aids and equipment however this is not of particular interest within the study, hence the simpler version will be used.

A recent review of specific health related quality of life instruments for venous leg ulcers favours the Charing Cross Venous Leg Ulcer Questionnaire (appendix 2) (Smith *et al* 2010) above others such as the Hyland for its disease specific psychometric characteristics (Gonzalez & Verdu 2011).

During the recruitment process the research team acts as a contact point and coordinator for patients requiring information and support. If concerns are raised on participants (mental) wellbeing based on the home visits or outcome of the assessments, referral of patients/families on to other professional agencies will be done as appropriate and according to the Trust guideline.

5.4 **Follow-up**

Patients are in the study until the VLU is healed or for the maximum period of 12 weeks. The patient will be followed up as they would in normal clinical practice. The community nurse will redress the VLU as per routine care, and will conduct the measurement of the VLU (grid measurement and PUSH score). The researcher will visit the patient at baseline, week 6 and week 12 of study participation to randomise the patient, hand out the StepIt pedal, measure ankle range of motion and conduct the questionnaires.

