6. SUBJECTS

6.1 Anticipated number of research subjects

Since there is no pilot data to base an *a priori* sample size calculation on, it is difficult to make a calculated prediction on the exact number of patients required for a sufficiently powered trial. The outcome of this present study will inform the power calculation for a larger definitive interventional trial. However, below a summary is given for the power potentially achievable for our suggested feasibility sample size. Since some patients may require surgical intervention or may withdraw, a hypothetical 30% dropout rate is calculated into the sample size (actual attrition rate is a study objective). A 1:1 allocation to the control and intervention group respectively will be applied.

The primary outcome, average percentage decrease in ulcer size is used for sample size calculation. Power calculations for sample size, 80% power and 5% significance, based on a Chi-squared test. A priori power calculations using GPower 3.1 software, result in the following sample size summarized in Table 4.

It must be stressed that this current PREVUE study will first and foremost establish if StepIt exercise is acceptable to staff and patients alike, and therefore it is not certain at this stage whether sufficient participants will be enrolled, if participants will be compliant and if they will be compliant for the 12 weeks treatment period.

Table 4, Sample size calculation

	Percentage patients achieving at least 50% reduction in ulcer size	Percentage patients not achieving 50% reduction in ulcer size		
Arm A (hypothetical)	60%	40%		
Arm B (hypothetical)	30%	70%		
	Power beta of 80%, Alpha p-value of 0.05, Effect size 0.6 Sample size required without any drop-out: 22 samples. Sample size with 30% attrition rate included: 28			
	Total of 28 patients: - 12 Patients to receive treatm - 12 Patient to receive treatment	nent as usual ent as usual plus Steplt exercise		

The CONSORT guidelines require a statement on the number of patients assessed for eligibility (Schulz, Altman & Moher 2010). The number of patients screened but who did not meet the inclusion criteria or who declined to participate will be recorded, as will any patients who are lot to follow-up (Appendix 3).

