The calculation does take into account a 30% patient attrition rate (withdrawal and loss to follow-up), since this involves a study with at least two visits. Patients will be recruited from the adult (age 18+) population routinely seen by the evaluating clinical staff members.

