6.3 Early withdrawal of subjects

Patients have the right to withdraw from the trial at any time and without giving any reason. If a patient withdraws from the trial, any and all information gathered prior to the withdrawal will be excluded in the analysis, no further data collection will occur. If a patient does not attend a planned follow-up appointment then two more attempts will be made to contact the patient regarding the study. If still no contact can be made then the patient is deemed lost to follow-up and any collected study data will be retained.

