8.2 Primary outcome statistics

The primary objective for this pilot study is the feasibility of conducting a larger scale randomised controlled trial. The secondary outcome statistics will inform the success of this pilot study and will therefore inform whether a larger scale trial is indicated. This will be based on signs of clinical effectiveness, positive patient feedback on the intervention, positive changes in VLU related quality of life, recruitment to time and target, low attrition rates, minimal data queries and lack of or low number of adverse events. If the effect size of the Steplt pedal is large enough, then this pilot trial may provide a definitive answer concerning its clinical effectiveness.

The following descriptive statistics will be reported on:

- Number of patients screened
- Number of patients eligible/ineligible, and percentage of patients consented into the trial
- Number of patients completed the trial/discontinued (plus reasons if discontinued)

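### Device feedback is promised at 6 and 12 weeks but scheduled at discharge, so patients who leave early would usually be missing from the section 8.2 feedback criterion

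*Protocol*

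**What the plan says.** **When feedback is due.** The secondary objective in the protocol summary reads "To determine the acceptability and efficacy of the step-it pedal as an adjuvant therapy for VLU at 6 and 12 weeks post-baseline", and the list under it includes what patients think of using the device. In the body, section 5.3 says "At their discharge visits participants are asked to provide their opinion on trial participation". Table 3 marks weeks 0, 6 and 12 for the ulcer, mobility, ankle, pain and quality-of-life measures but has no row for opinion or feedback. Appendix 1 lists no feedback form.

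**Visits and planned exit.** Section 5.4 says "The researcher will visit the patient at baseline, week 6 and week 12 of study participation", and also "Patients are in the study until the VLU is healed or for the maximum period of 12 weeks".

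**Patients who leave early.** Section 6.3 says "If a patient withdraws from the trial, any and all information gathered prior to the withdrawal will be excluded in the analysis, no further data", and the sentence goes on to rule out later collection. A patient who cannot be reached after two further attempts is treated as lost to follow-up; data already collected are kept. Section 6.1 says "a hypothetical 30% dropout rate is calculated into the sample size (actual attrition rate is a study objective", and later defines what this covers: "The calculation does take into account a 30% patient attrition rate (withdrawal and loss to follow-up".

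**How feedback is used.** Section 8.2 names "positive patient feedback on the intervention" as one of seven considerations that inform whether a larger trial is indicated. It gives no threshold. It also reports how many patients discontinued, with reasons.

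**The concern.** The summary and the body disagree on when feedback is taken. If the body is followed, the question is put at the end of participation, and patients who leave before then are usually not asked. Leaving may be related to how a patient finds the exercise, so the responders may be a favourable selection.

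Acceptability is a central purpose of this study: section 6.1 says that it must first show whether the exercise is acceptable to staff and patients. A feedback result drawn mainly from patients who stayed could look better than the experience of everyone given the pedal. When data are collected is fixed in the protocol, and a later analysis plan cannot recover feedback that was never requested or that section 6.3 orders to be dropped.

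**Working it through.** **1. The passages side by side.**

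| Source | What it fixes |
|---|---|
| Summary, secondary objectives | Device feedback sits under an objective timed at 6 and 12 weeks |
| Section 5.3 | Opinion asked at the discharge visit |
| Table 3 | No feedback row at any week |
| Section 5.4 | Researcher visits at baseline, week 6 and week 12 |
| Section 6.3, withdrawal | Earlier data excluded, later collection stopped |
| Section 6.3, lost to follow-up | Earlier data kept, no further contact |
| Section 8.2 | Positive feedback is a criterion, with no threshold |

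Under the section 5.3 schedule, neither group of early leavers ordinarily supplies feedback. Patients discharged early because the ulcer has healed can still be asked, so they are not counted as missing here.

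If a week-6 question were added and section 6.3 left as it is, week-6 answers would be kept for patients later lost to follow-up but discarded for patients who later withdraw. Both sections have to change together.

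**2. The protocol's own sample size.** For a chi-squared test with 1 degree of freedom, effect size 0.6, alpha 0.05 and 80% power, the total is 22, which matches Table 4. The 28 corresponds to 22 × 1.3 = 28.6, without the fraction; dividing by the retained share would give 22 / 0.7 = 31.4, so 32. This affects the present point only through arm size. Table 4 totals 28 but lists 12 + 12 = 24, and the lay summary has 24 per arm, so all three arm sizes are shown.

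**3. How many StepIt patients would give no feedback.** Missing = arm size × 0.30.

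- 14 per arm (28 at 1:1): 14 × 0.30 = 4.2, about 4 missing and 10 responding.
- 12 per arm: 12 × 0.30 = 3.6, about 4 missing and 8 responding.
- 24 per arm: 24 × 0.30 = 7.2, about 7 missing and 17 responding.

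**4. Bounds if every responder is positive** (an assumption chosen for illustration). The lower bound counts no leaver as positive, the upper bound counts all of them. Intervals are exact (Clopper-Pearson) 95%.

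| StepIt arm | Responders only | Lower bound, all randomised | Upper bound |
|---|---|---|---|
| 14 | 10/10 = 100% (69–100%) | 10/14 = 71% (42–92%) | 14/14 = 100% |
| 12 | 8/8 = 100% (63–100%) | 8/12 = 67% (35–90%) | 12/12 = 100% |
| 24 | 17/17 = 100% | 17/24 = 71% | 24/24 = 100% |

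**5. General form.** Share among all randomised = 0.7 × c + 0.3 × d, where c is the positive rate in responders and d the rate in leavers. For an assumed c = 90%:

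- d = 0: 0.7 × 0.90 = 63%.
- d = 50%: 0.63 + 0.15 = 78%.
- d = 90%: 0.63 + 0.27 = 90%, so no bias.
- d = 100%: 0.63 + 0.30 = 93%.

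The documents give neither c nor d, so they support a range and not a single estimate of bias.

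**The case against.** **Section 5.3 does not say that opinion is asked at discharge and at no other time.** This stands. Read with the summary and the week-6 visit, it is a timing conflict to reconcile and not a settled decision to ask completers alone. But no other collection point is scheduled, so a site following section 5.3 and Table 3 would not ask at week 6. The discharge visit is also undefined, so some patients whose management changes may still be asked.

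**Leavers already count in the decision.** Section 8.2 lists low attrition beside feedback and reports reasons for discontinuation; section 5.5.1 makes attrition and compliance primary outcomes. This stands, and it is why non-responders should not be scored as negative in the main figure. It does not remove the gap: attrition shows how many left, not what they thought of the pedal, and sections 5.2 and 6.3 let patients leave without giving a reason.

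**Stopping the exercise is not leaving the trial.** This stands in part. Section 8.3 groups StepIt patients by how closely they followed the exercise, so some who exercise little are expected to stay, and section 6.1 names surgery as a cause of dropout, which says nothing about the device. Selection on dislike of the exercise is plausible but not shown.

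**The question in 5.3 concerns trial participation, while 8.2 concerns the intervention.** The link is indeed inferred. If the two are different items, however, device feedback has no scheduled collection at all.

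**The denominator belongs in the analysis plan.** That is fair for the denominator alone. It does not answer the collection schedule or the exclusion rule in section 6.3, both of which this protocol fixes.

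**Conclusion.** The point holds as a timing conflict with a foreseeable selection effect. Followed as written, the body would base the feedback criterion mainly on patients who reach discharge, and this may overstate acceptability. With 14 StepIt patients, 30% attrition and 10 positive responders out of 10, the share among all randomised lies anywhere from 71% to 100%. This rests on the 30%, which the protocol calls hypothetical, and on leavers having no discharge visit at which they are asked.

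A reader might infer a 29-point overstatement (100% less 71%), or that the progression decision would be reversed. The documents support neither. The 29 points are one extreme, and the difference is zero if leavers feel as responders do. Section 8.2 sets no cut-off for feedback, and it weighs feedback with six other considerations, attrition among them, so the effect on the decision cannot be quantified. This is a worthwhile, low-cost improvement and not a flaw that invalidates the study.

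**What to change.** 1. **Section 5.3 and Table 3:** reconcile them with the summary. Add a short question on the device, for the StepIt arm, at the existing week-6 researcher visit as well as at discharge, and give it a row in Table 3. Word it so that it asks about the intervention, which is what section 8.2 uses.
2. **Section 6.3:** amend so that feedback given before withdrawal is kept, where consent allows. Without this, the week-6 question would not help for patients who withdraw.
3. **Section 8.2:** report positive feedback with both the number responding and the number randomised to StepIt. Put the responders-only figure beside the bound that counts non-responders as not positive, labelled as a sensitivity range. That bound should not be the main figure, because some patients leave for reasons unrelated to the device and attrition is already a separate criterion.

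The cost is one extra question at a visit that already takes place, some protocol wording, and a lower bound that looks less favourable.
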